4.2 Rationale

4.2.1 Rationale for the Trial and Selected Subject Population

The trial is a randomized, placebo-controlled, parallel-group, multicenter and 16 weeks of double-blinded trial, and subsequent of 36 weeks open-label extension trial of omarigliptin in Japanese subjects with T2DM who have inadequate glycemic control on insulin monotherapy in addition to diet and exercise therapy.

Recently, insulin self-injection is widely used for T2DM in addition to type 1 DM since environment of insulin therapy is dramatically improved by insulin formulation, devise was improved and/or self-monitoring blood glucose (SMBG) was familiarized. Additionally, insulin therapy is widely used combination with variant DPP-4 inhibitors [1] [2].

Omarigliptin was launched in November 2015, and it is anticipated to be used with insulin therapy similar to other marketed DPP-4 inhibitors. However, a clinical trial in which omarigliptin and insulin are used in combination to assess safety and efficacy has not yet been conducted.

Based on the above, the trial will be conducted as one of pharmacovigilance activities and investigation/study for assessment of efficacy in order to examine the safety and efficacy of omarigliptin, weekly DPP-4 inhibitor, in Japanese subjects with T2DM who have inadequate glycemic control on insulin monotherapy.

4.2.2 Rationale for Dose Selection/Regimen

Dosage and administration of omarigliptin was approved in Japan as “usually, for adults, 25 mg of omarigliptin is orally administrated once weekly”. In this study, the dosage and administration is set as omarigliptin 25 mg per week according to the Japan Label.

4.2.2.1 Rationale for the Use of Placebo

4.2.2.1.1 Rationale for the use of placebo for the pre-treatment period

To exclude subjects who are unlikely to comply with the administration of study drug before entry into the treatment period, a 2-week placebo run-in period is designed into the pre-treatment period.

4.2.2.1.2 Rationale for the use of placebo for the treatment period

In addition to comparison between pre-dose and post-dose, comparison between omarigliptin 25 mg q.w. group and placebo group enables an exclusion of influences of the subject population, changes over time, and other factors, and an accurate characterization of the glycemic control potential of omarigliptin. In addition, the variability in any measurements in patients with T2DM requires a placebo group to adequately characterize any potential positive/negative effects of omarigliptin in patients with T2DM. Considering the importance of this study in adequately characterizing the efficacy and safety of omarigliptin for 16 weeks, the placebo group is designed into the treatment period.

4.2.2.2 Rationale for Duration of Treatment Period

To assess the long-term safety of omarigliptin when administered with insulin, the treatment period is defined as 52 weeks based on the “Guideline on Clinical Evaluation Methods for Oral Hypoglycemic Agents”, MHLW Pharmaceutical and Food Safety Bureau (PFSB), Draft, 19th May 2014 [11](hear after “Guideline draft”). For efficacy assessment, the Guideline draft [11] recommends having 12-24 weeks double-blinded period in which dosage and administration of insulin is maintained in principle. The rationales of 16 weeks for the double-blinded placebo-controlled period for the study are followings; (1) based on the results of previous studies with omarigliptin conducted in Japan, 16 weeks will provide sufficient time to observe the maximal reduction in HbA1c with omarigliptin and (2) it minimizes the duration of the use of placebo.

4.2.3 Rationale for Endpoints

4.2.3.1 Efficacy Endpoints

HbA1c, the primary endpoints, is recommended as a parameter during the double-blind period (during the period dosage and administration of insulin shall be stable) in long-term trial of co-administration of insulin and oral AHAs in Guideline draft [11].

The Treatment Guide for Diabetes [1] states that HbA1c is an important parameter of glycemic control in patients, and the evaluation should be complemented with FPG etc.

Based on the above, the primary efficacy endpoint is change from baseline in HbA1c, the secondary efficacy endpoint is change from baseline in FPG.

In addition, 1, 5-AG reflects postprandial hyperglycemia, therefore, change from baseline in 1, 5-AG is added as a secondary efficacy endpoint.

4.2.3.2 Safety Endpoints

The following endpoints will be collected to assess the safety of omarigliptin when co-administered with insulin.

- Adverse events (including hypoglycemia)
- Vital signs (body weight, blood pressure, and pulse rate)
- Laboratory tests
- Electrocardiogram (ECG)

4.2.3.3 Future Biomedical Research

The Sponsor will conduct Future Biomedical Research on specimens consented for future biomedical research during this clinical trial. This research may include genetic analyses (DNA), gene expression profiling (RNA), proteomics, metabolomics (serum, plasma) and/or the measurement of other analytes, depending on which specimens are consented for future biomedical research.

Such research is for biomarker testing to address emergent questions not described elsewhere in the protocol (as part of the main trial) and will only be conducted on specimens from appropriately consented subjects. The objective of collecting/retaining specimens for Future Biomedical Research is to explore and identify biomarkers that inform the scientific understanding of diseases and/or their therapeutic treatments. The overarching goal is to use such information to develop safer, more effective drugs/vaccines, and/or to ensure that subjects receive the correct dose of the correct drug/vaccine at the correct time. The details of this Future Biomedical Research sub-trial are presented in Section 12.2 – Collection and Management of Specimens for Future Biomedical Research.

4.3 Benefit/Risk

Subjects in clinical trials generally cannot expect to receive direct benefit from treatment during participation, as clinical trials are designed to provide information about the safety and effectiveness of an investigational medicine.

Additional details regarding specific benefits and risks for subjects participating in this clinical trial may be found in the accompanying approved labeling and Informed Consent documents.

5.0 METHODOLOGY

5.1 Entry Criteria

5.1.1 Diagnosis/Condition for Entry into the Trial

Male or female Japanese subjects with T2DM at least 20 years of age who are have inadequate glycemic control on insulin monotherapy with or without single oral AHA in addition to diet and exercise therapy will be enrolled in this trial.

5.1.2 Subject Inclusion Criteria

In order to be eligible for participation in this trial, the subject must:

At Visit 1/Screening

- 1) Have T2DM
- 2) Be ≥ 20 years of age on the day of signing the informed consent form (ICF)
- 3) Meet all of following criteria for Group A or B at Visit 1/Screening:

Group A (pre-treatment period is 10 weeks)

- (1) Are currently treated with diet and exercise therapy, AND
- (2) Have been on a stable dosage and administration of insulin (8 to 40 units/day) for 4 weeks or longer, AND

<Note> Insulin will be administered during the trial as monotherapy of premixed insulin/fixed ratio combination of insulin (content percentage of rapid-acting or ultra rapid-acting insulin is lower than or equal to 30%), intermediate or long-acting insulin. If a subject is treated with the insulin monotherapy on the consent date, but the dosage of insulin was modified within 4 weeks before on the consent date, it can be allowed to postpone Visit 1/Screening until the subject meets the requirement. In this case, the type of insulin, and the dosage and administration should not be changed/modified from those on the consent date.

- (3) Have been on a single oral AHA, AND

<Note> Wash-out from multiple oral AHAs is not allowed in the trial.

- (4) Are not on any injectable AHA, except insulin monotherapy, AND
- (5) HbA1c $\geq 7.0\%$ and $\leq 9.0\%$

Group B (pre-treatment period is 2 weeks)

- (1) Are currently treated with diet and exercise therapy, AND

(2) Have been on a stable dosage and administration of insulin (8 to 40 units/day) for 10 weeks or longer, AND

<Note> Insulin will be administered during the trial as monotherapy of pre-mixed insulin/fixed ratio combination of insulin (content percentage of rapid-acting or ultra rapid-acting insulin is lower than or equal to 30%), intermediate or long-acting insulin. If a subject is treated with the insulin monotherapy on the consent date, but the dosage of insulin was modified within 10 weeks before on the consent date, it can be allowed to postpone Visit 1/Screening until the subject meets the requirement. In this case, the type of insulin, and the dosage and administration should not be changed/modified from those on the consent date.

(3) Have not been on any additional AHAs (except for insulin monotherapy) in the past 8 weeks, AND

(4) HbA1c $\geq 7.5\%$ and $\leq 10.0\%$

4) Have a body mass index (BMI) $> 18 \text{ kg/m}^2$ and $< 40 \text{ kg/m}^2$

5) Meets one of the following criteria:

(1) Subject is a male

(2) Subject is a female not of reproductive potential defined as one who has either

a) Reached natural menopause (defined as ≥ 12 months of spontaneous amenorrhea in women ≥ 45 years of age), or

b) Had bilateral oophorectomy and/or hysterectomy, or had bilateral tubal ligation at least 8 weeks prior to Visit 1/Screening.

(3) Subject is a female of reproductive potential and:

a) Agrees to remain abstinent from heterosexual activity, or

b) Agrees to use (or have their partner use) acceptable contraception to prevent pregnancy within the projected duration of the study and for 21 days after the last dose of study medication. Acceptable methods of contraception include:

(a) Use of double-barrier methods; diaphragm with spermicide and a condom.

(b) Use of hormonal contraception (any registered and marketed contraceptive agent that contains an estrogen and/or a progestational agent [including oral, subcutaneous, intrauterine and intramuscular agents, and cutaneous patch]) with one of the following: diaphragm with spermicide; condom; vasectomy; or intrauterine device (IUD).

(c) Use of an IUD with one of the following: condom; diaphragm with spermicide; vasectomy; or hormonal contraception (see above).

(d) Vasectomy with one of the following: diaphragm with spermicide; condom; IUD; or hormonal contraception (see above).

6) Understand the study procedures, alternative treatments available, and risks involved with the study, and voluntarily agrees to participate by giving written informed consent. The subject may also provide consent for Future Biomedical Research (FBR). However, the subject may participate in the main trial without participating in FBR.

At Visit 3/Week -2

7) Be treated with diet and exercise therapy ≥ 39 days (6 weeks -3 days)

<Note> See Section 6.0 trial flow chart for scheduling Visit 3/Week -2. Compliance with diet and exercise therapy will be assessed comprehensively throughout the above period. In the case of exercise therapy, this condition does not necessarily need to be met if it is judged to be inappropriate for a subject because of complication[s].

8) Be on a stable dosage and administration of insulin ≥ 67 days (10 weeks -3 days)

9) Not be on other AHAs except for insulin monotherapy ≥ 53 days (8 weeks -3 days)

10) Meet all following glycemic criteria at Visit 3/Week -2

(1) HbA1c $\geq 7.5\%$ and $\leq 10.0\%$

<Note> If subjects in Group B performed the procedures of Visit 3/Week -2 within 2 weeks after Visit 1/Screening, HbA1c measurement is not needed at Visit 3/Week -2. The subject may be deemed to meet the HbA1c criterion of Visit 3/Week -2 by HbA1c value of Visit 1/Screening

(2) FPG ≥ 126 mg/dL and ≤ 230 mg/dL

<Note> FPG may be re-tested once upon the investigators discretion if he/she believes that the value does not reflect the subject's recent glycemic control.

At Visit 4/Day 1/Randomization

11) Be treated with diet and exercise therapy ≥ 53 days (8 weeks -3 days)

<Note> See Section 6.0 trial flow chart for scheduling Visit 4/Day 1/Randomization. Compliance with diet and exercise therapy will be assessed comprehensively throughout the above period. In the case of exercise therapy, this condition does not necessarily need to be met if it is judged to be inappropriate for a subject because of complication[s].

12) Be on a stable dosage and administration of insulin ≥ 81 days (12 weeks -3 days)

13) Not be on AHAs except for insulin monotherapy ≥ 67 days (10 weeks -3 days)

14) Have 100% compliance with study medication (placebo) which is confirmed by counting remaining tablets at the trial site, and Have $\geq 85\%$ compliance with insulin during the single-blind placebo run-in period (From the day at Visit 3/Week -2 to the day before Visit 4/Day 1/Randomization).

5.1.3 Subject Exclusion Criteria

The subject must be excluded from participating in the trial if the subject:

<Note> Subjects with laboratory screening values meeting protocol exclusion criteria may, at the discretion of the investigator, have one repeat determination performed by the central laboratory. If the repeat value does not meet the criterion, the subject may continue in the screening process. Only laboratory tests meeting exclusion criteria are to be repeated (not the entire panel). Note that repeat determination can be performed only once for each laboratory test during the Screening and Pre-treatment Period.

At Visit 1/Screening

Criteria related to Diabetes

- 1) Has type 1 DM or has a history of diabetic ketoacidosis.
- 2) Has a history of being administered any of the following AHAs including fixed dose combination (FDC) containing the following ingredients:
 - (1) TZD: within 12 weeks prior to Visit 1/Screening
 - (2) GLP-1 receptor agonists: within 12 weeks prior to Visit 1/Screening
 - (3) Omarigliptin (including placebo for treatment period): any time

<Note> Subjects who have previously participated in clinical studies with omarigliptin but were not enrolled into the active treatment period (i.e., only took single-blinded placebo during the observation period) may be eligible to participate in the trial.

- 3) Has history of severe hypoglycemia with coma or loss of consciousness, or for whom hypoglycemia was observed greater or equal to two times per week within 8 weeks prior to Visit 1/Screening.

Requiring Specific Treatments

- 4) Is currently participating in or has participated in another study with an investigational compound or device within the prior 12 weeks of Visit 1/Screening and does not agree to refrain from participating in any other study while participating in this study.

<Note> A subject who has participated in a non-interventional study may be enrolled.

- 5) Has undergone a surgical procedure within 8 weeks prior to Visit 1/Screening or has planned major surgery during the study.

<Note> A subject who has undergone minor surgery within the prior 8 weeks and is fully recovered or a subject who has planned minor surgery may participate. Minor surgery is defined as a surgical procedure involving local anesthesia.

- 6) Receives a following medication at unstable dosage and administration:
 - (1) Lipid-lowering medication: within 4 weeks prior to Visit 1/Screening
 - (2) Thyroid hormone replacement therapy : within 6 weeks prior to Visit 1/Screening
- 7) Is currently on or likely to require treatment with a prohibited medication (refer to 5.5.1), and/or subject has unstable complication such as he/she is likely to require a new treatment and/or adjustment with a limited concomitant medication.

Concomitant Disease of Organs and Systems

- 8) Has poorly controlled hypertension defined as systolic blood pressure of ≥ 160 mmHg or diastolic blood pressure of ≥ 90 mmHg and blood pressure is unlikely to be within these limits by Visit 3/Week -2 with an adjustment in anti-hypertensive medication (See section 5.5.2).

<Note> Investigators are encouraged to maximize blood pressure control. Subject may have blood pressure medications adjusted and be enrolled if repeat blood pressure measurement no longer meets exclusion criterion.
- 9) Has a medical history of active liver disease (other than non-alcoholic hepatic steatosis), including chronic active hepatitis B or C (assessed by medical history), primary biliary cirrhosis, or symptomatic gallbladder disease.
- 10) Has human immunodeficiency virus (HIV) as assessed by medical history.
- 11) Has had new or worsening signs or symptoms of coronary heart disease or congestive heart failure within the past 3 months, or has any of the following disorders within the past 3 months:
 - (1) Acute coronary syndrome (e.g., myocardial infarction or unstable angina)
 - (2) Coronary artery intervention (e.g., coronary artery bypass grafting or percutaneous transluminal coronary angioplasty)
 - (3) Stroke or transient ischemic neurological disorder
- 12) Has severe peripheral vascular disease (e.g., claudication with minimal activity, a nonhealing ischemic ulcer, or disease which is likely to require surgery or angioplasty).
- 13) Has a history of malignancy ≤ 5 years prior to Visit 1/Screening, except for adequately treated basal cell or squamous cell skin cancer, or in situ cervical cancer.

<Note> The following subjects should be excluded;

 - (1) A subject with a history of malignancy >5 years prior to Visit 1/Screening should have evidence of residual or recurrent disease
 - (2) A subject with any history of melanoma, leukemia, lymphoma, or renal cell carcinoma.

14) Has a clinically important hematological disorder (such as aplastic anemia, myeloproliferative or myelodysplastic syndromes, thrombocytopenia).

Laboratory Abnormalities

15) Have any exclusionary laboratory values as listed in [Table 1](#) below.

Table 1 Laboratory Exclusion Criteria (Visit 1/Screening)

Parameter	Population	Study Limit for Exclusion
Estimated glomerular filtration rate (eGFR) ¹		<35 mL/min/1.73 m ²
Alanine aminotransferase (ALT)		>two times upper limit of normal (ULN)
Aspartate aminotransferase (AST)		>two times ULN
Thyroid-stimulating hormone (TSH)		Outside central laboratory normal range
Hemoglobin	Male	<11 g/dL
	Female	<10 g/dL
Triglyceride		>600 mg/dL
C-peptide		<0.6 ng/mL

¹ eGFR (mL/min/1.73 m²) = 194 x serum creatinine (Cr)^{-1.094} x age (years)^{-0.287} (x 0.739 for female).

Insulin therapy-Specific Criterion

16) Meets any contraindication or warning listed on the package insert of each insulin products and which do not be contained in the exclusion criteria of this study protocol.

Other Criteria

17) (For women of childbearing potential) has a positive urine pregnancy test.

18) Meets any following criteria regarding pregnant, breast-feeding or donate eggs;

- (1) Be pregnant or breast-feeding
- (2) Is expecting to conceive during the study, including 21 days following the last dose of study medication.
- (3) Subject is expecting to undergo hormonal therapy in preparation to donate eggs during the period of the trial, including 21 days following the last dose of study medication.

19) Is a user of recreational or illicit drugs or has had a recent history of drug abuse.

20) Meets any following criteria regarding alcohol consumption;

- (1) Routinely consumes >14 alcoholic drinks per week
- (2) Engages in binge drinking ["Binge drinking" is defined as a pattern of 5 or more alcoholic drinks (male), or 4 or more alcoholic drinks (female) in about 2 hours].

<Note> One alcoholic drink is defined as 5 oz (150 mL) of wine, or 12 oz (350 mL) of beer, or 1.5 oz (45 mL) of 80 proof liquor.

- 21) Meets any following criteria regarding donated blood products, phlebotomy or receive of blood products
 - (1) Has had phlebotomy of >300 mL or donated blood products of >300 mL within 8 weeks of Visit 1/Screening
 - (2) Has intends to have phlebotomy or donated blood products within the projected duration of the study
 - (3) Has received, or is anticipated to receive, blood products within 12 weeks of Visit 1/Screening or within the projected duration of the study.

- 22) Is disqualified from the study by the investigator for any reasons other than those given above.

Example: Subject has a history or current evidence of any condition, therapy, lab abnormality or other circumstance as follows,

- (1) Makes participation not in the subject's best interest,
- (2) Might interfere with the subject's participation for the full duration of the study,
- (3) Might confound the results of the study.

- 23) Is or has an immediate family member (e.g., spouse, parent/legal guardian, sibling or child) who is investigational site or sponsor staff directly involved with this trial.

At Visit 2/Week -10 (Only for Group A)

Other Criterion

- 24) Is disqualified from the study by the investigator for any reasons other than those given above.

At Visit 3/Week -2

Concomitant Disease of Organs and Systems

- 25) Has poorly controlled hypertension defined as systolic blood pressure of ≥ 160 mmHg or diastolic blood pressure of ≥ 90 mmHg.

Laboratory Abnormalities

- 26) Has any exclusionary laboratory values as listed in [Table 2](#) below.

Table 2 Laboratory Exclusion Criteria (Visit 3/Week -2)

Parameter	Population	Study Limit for Exclusion
eGFR ¹		<35 mL/min/1.73 m ²
ALT		>two times ULN
AST		>two times ULN
Triglyceride		>600 mg/dL

¹ eGFR (mL/min/1.73 m²) = 194 x serum Cr^{-1.094} x age (years)^{-0.287} (x 0.739 for female).

Other Criteria

- 27) (For women of childbearing potential) have a positive urine pregnancy test.

28) Be disqualified from the study by the investigator for any reasons other than those given above.

At Visit 4/Day 1/Randomization

Criteria related to Diabetes

29) Is difficult to continue stable dosage and administration of insulin during Phase A (double-blind period, 16 weeks)

30) Received rapid-acting or ultra rapid-acting insulin within 10 weeks prior to Visit 4/Day 1/Randomization.

31) Received pre-mixed insulin/fixed ratio combination of insulin with a greater than 30% rapid or ultra rapid-acting insulin within 10 weeks prior to Visit 4/Day 1/Randomization.

32) Has history of severe hypoglycemia with coma or loss of consciousness, or for whom hypoglycemia was observed greater or equal to two times per week from Visit 1/Screening to Visit 4/Day 1/Randomization.

Other Criteria

33) (For women of childbearing potential) have a positive urine pregnancy test.

34) Be disqualified from the study by the investigator for any reasons other than those given above.

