5.5.1 Prohibited medications

- (1) All AHAs (Except for omarigliptin for the trial and insulin agents which will be administered during the trial)
 - a) Insulin agents [rapid-acting, ultra rapid-acting insulin or pre-mixed insulin/fixed ratio combination of insulin (content percentage of rapid-acting or ultra rapid-acting insulin is greater than 30%)]
 - b) SUs (sulfonylureas, sulfonamides)
 - c) Glinides (nateglinide, mitiglinide, repaglinide, etc.)
 - d) BGs
 - e) TZD
 - f) α -GIs
 - g) DPP-4 inhibitors
 - h) SGLT2 inhibitors
 - i) GLP-1 receptor agonists (Such as exenatide or liraglutide)
 - j) FDC products containing the above active ingredient(s) (Except for insulin agents which will be administered during the trial)

<Note> The subject in Group A can continue single oral AHA taken at Visit 1/Screening thorough to Visit 2/Week -10.

- (2) Other investigational drugs

- (3) Systemic corticosteroids \geq 14 consecutive days or repeated courses

<Note> Inhaled, nasal, and topical corticosteroids which don't have systemic effect are permitted.

Within 10 hours before the visit

- (1) Intravenous fluids (other than those having a volume <50 mL without any glucose content)
- (2) Glucagon

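### Exclusion 4 joins its two conditions with 'and', so a recently completed non-AHA investigational drug or device study does not exclude a subject who agrees to refrain from other studies

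*Combined protocol and SAP*

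**What the plan says.** Exclusion 4 in Section 5.1.3 has two limbs. The first is participation: "Is currently participating in or has participated in another study with an investigational compound or device within the prior 12 weeks of Visit 1/Screening". The second follows in the same sentence: "and does not agree to refrain from participating in any other study while participating in this study". A note beneath adds one exception: "A subject who has participated in a non-interventional study may be enrolled".

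Related rules elsewhere are:
- **Section 5.5.1, item (2)** lists "Other investigational drugs" among prohibited medications. Exclusion 7 removes anyone who is on a prohibited medication at screening or is likely to need one.
- **Exclusion 2** bars TZDs and GLP-1 receptor agonists for 12 weeks before Visit 1. It also bars previous treatment-period exposure to the study drug: "Omarigliptin (including placebo for treatment period): any time".
- **Section 5.1.2** requires of Group B at screening: "Have not been on any additional AHAs (except for insulin monotherapy) in the past 8 weeks". Inclusions 9 and 13 require all subjects to be free of AHAs other than insulin for at least 53 days at Week -2 and at least 67 days at randomization.
- **Exclusion 22** is a discretionary catch-all: "Is disqualified from the study by the investigator for any reasons other than those given above". It is repeated at later visits as exclusions 24, 28 and 34.

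**The concern.** A criterion built on a 12-week look-back should exclude on that look-back alone. With 'and', the look-back takes effect only in a subject who also refuses to stay out of other studies, and the refusal takes effect only in a subject with recent participation. Neither protection works by itself.

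Two things are at stake. A subject may be randomized with residual effects of another product, and an adverse event in that subject is then hard to attribute. This matters because safety and tolerability are primary objectives (Section 3.1), and the 52-week safety summaries make no between-group comparison (Section 8.6.2). Sites may also apply the rule differently, some by its letter and some by its evident purpose.

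**Working it through.** The plan gives no figure to reproduce here. The check is one of logic, then a search for another rule that closes the gap, then the visit timing.

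**1. Truth table.** Let P be current or 12-week prior participation in an investigational study, and R be not agreeing to refrain.

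| P | R | Excluded with 'and' (as written) | Excluded with 'or' |
|---|---|---|---|
| yes | yes | yes | yes |
| yes | no | **no** | yes |
| no | yes | **no** | yes |
| no | no | no | no |

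As written, 1 of 4 combinations is excluded; with 'or', 3 of 4. The second and third rows are the gap.

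**2. Which reading was meant.** The note admits subjects from non-interventional studies. Such an exception is needed only if interventional participation excludes by itself. Exclusion 5, the next item, has the same past-and-future structure (recent surgery, planned surgery) and joins its parts with 'or'. Both point to 'or'.

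**3. Whether another rule closes the gap.**

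| Rule | Covers | Leaves open |
|---|---|---|
| Exclusion 7 with 5.5.1(2) | Investigational drug in use, or likely to be needed | A drug already stopped; devices |
| Exclusion 2 | TZD, GLP-1 receptor agonist, omarigliptin | All other compounds |
| Group B rule, inclusions 9 and 13 | AHAs, including investigational ones | Non-AHA compounds; devices |
| Exclusions 22, 24, 28, 34 | Anything the investigator chooses | Not a rule |

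The AHA rules set a minimum AHA-free interval rather than a 12-week window before Visit 1, so their cover is large but not complete. No other section restates a 12-week washout for investigational products. Section 7.1.1.5.1 asks for non-AHA prior medication over only 6 weeks, so a non-AHA compound stopped 6 to 12 weeks before Visit 1 falls outside that record.

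**4. Timing.** Take a subject who stopped a non-AHA investigational compound 7 days before Visit 1 and agrees to refrain. The intervals come from Sections 6.0, 7.1.5.1 and 7.1.5.2. The lower ends assume no delay after Visit 1 and are bounds.
- Group B, last dose to randomization: 7 + (0 to 14) + (14 to 17) = 21 to 38 days.
- Group A: 7 + (0 to 14) + (53 to 59) + (14 to 17) = 74 to 97 days.
- If the 12-week window had force of its own, the minimum in Group B would be 84 + 0 + 14 = 98 days.

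**5. Effect on the primary comparison.** Exposure before screening precedes randomization. Allocation is random in a 2:1 ratio and Phase A is double-blind, so the proportion exposed has the same expectation in both arms. The expected bias in the between-arm HbA1c difference is about zero.

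**The case against.** The strongest reply is that the protocol already protects against most of what a reader might infer from the 'and'.

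- **Overlapping drugs.** A reader might infer that subjects could enter while still taking another investigational drug. The documents do not support this: exclusion 7 with Section 5.5.1(2) excludes them whatever exclusion 4 says. The same prohibition applies during the trial to a subject who refused to refrain, and Section 5.8 gives need for an excluded medication as an example of a reason to discontinue. This stands, and it limits the reverse gap mainly to devices and drug-free studies.
- **Biased HbA1c result.** A reader might infer that carry-over distorts the primary estimate. The AHA rules remove most agents likely to carry a glycemic effect, and randomization balances the remainder in expectation. This also stands.
- **Evident intent.** The note makes the purpose recoverable, so many sites would probably apply 'or'. That is plausible, but an eligibility rule should not depend on it. The conjunction in the Japanese version cannot be seen here. The Summary of Changes shows that the two language versions have differed in the wording of exclusion criteria.
- **A one-word swap.** A reader might infer that changing 'and' to 'or' is enough. It is not. The second limb refers to any other study, and the note covers only past participation, so a subject unwilling to give up a registry would be newly excluded.

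None of these points restores the 12-week rule for a completed non-AHA compound or for a device.

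**Conclusion.** The point holds, within limits. Exclusion 4 as worded admits subjects it was evidently meant to exclude, and for completed non-AHA exposure or device participation within 12 weeks of Visit 1 only investigator discretion stands in the way. The agreement to refrain is likewise not required of a subject with no recent participation.

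The consequence is minor. The documents do not say how many subjects would be affected, so no count is offered. Sample size and power are unaffected. The case for correction rests on subject protection, attribution of adverse events, and uniform eligibility. It assumes that the English text is applied literally and that the Japanese version carries the same conjunction.

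**What to change.** Split exclusion 4 into two independent criteria joined by 'or':
- (a) the subject is in, or within 12 weeks before Visit 1 was in, another study of an investigational compound or device; or
- (b) the subject does not agree to stay out of any other interventional study for the duration of this trial.

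Let the non-interventional note apply to both (a) and (b). Check the Japanese version for the same conjunction and correct both versions together. While doing so, reconcile the 12-week window with the 6-week look-back for non-AHA medication in Section 7.1.1.5.1, so that sites have a record against which to check (a).

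The cost is a short wording change in an amendment and a very small loss of eligible subjects.
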